6.5 Analyses Addressing Exploratory Study Endpoints

The exploratory endpoints in Section 3.3 will be assessed and results will be described.

7.0 SUBGROUP ANALYSES

For the primary outcome measure in Section 3.1 and secondary outcome measures (a-f) in Section 3.2, subgroup analyses by prior TNFi exposure (TNFi-naïve and TNFi-exposed prior to Visit 2) will be performed for the eligible patients who meet inclusion and exclusion criteria and initiated the study treatment.

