The goal of precision medicine is to match patients with a treatment MOA that most closely matches his or her individual disease biology to improve disease outcomes in a timely fashion. Precision medicine has been most successful in oncology where genetic (DNA) changes in patient tumors are analyzed in order to identify the best treatment options for each individual. However, DNA data alone is insufficient to determine individual treatment options in complex diseases such as RA. Scipher Medicine is using network medicine and artificial intelligence to

bring precision medicine to complex diseases through a combined analysis of gene expression (RNA) data, clinical metrics, and appropriate laboratory markers. PrismRA® is the first test developed using Scipher's network medicine approach.

PrismRA was developed because the majority of RA patients receive a TNFi therapy as their b/tsDMARD^{7,8}. It is a molecular signature test designed to predict the likelihood that a RA patient will be a non-responder to TNFi therapies. From a single blood draw taken before the start of treatment, the PrismRA test assesses twenty-three (23) biomarkers that are integrated into a single predictive model that generates a score on a scale of one (1) to twenty-five (25) that represents the likelihood of non-response to TNFi therapies. In a prior PrismRA validation study, patients with a molecular signature of non-response were less likely to have an adequate response to TNFi therapies than those patients lacking the signature according to ACR50, ACR70, CDAI, and DAS28-CRP with significant odd ratios of 3.4-8.8 for targeted therapy naïve patients and 3.3-26.6 for TNFi-exposed patients¹⁰.

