5.0 GENERAL STATISTICAL CONSIDERATIONS

5.1 Sample Size and Power Calculations

The study is powered to detect a difference of 10% in the proportion of patients with improvement in CDAI from baseline to Week 24 by at least the MID as defined in Section 3.1 between the PrismRA arm and the external control arm. Results are shown in **Table 1**. It is estimated that the attrition rate at Week 24 (defined as the proportion of patients with missing CDAI scores at Week 24 for any reason) can be up to 45% in the PrismRA arm and up to 50% in the external control arm. The sample sizes below have been inflated accordingly to account for the patient attrition mentioned above.

With a sample size of 600 in the PrismRA arm and 1,500 in the external control arm, the study has 88% power to establish the superiority of the PrismRA intervention as compared to the standard of care by detecting a difference of 10% between the two study arms based on Fisher’s

exact test of independent proportions assuming the proportion of patients with improvement in CDAI by MID are 40% and 30% in the PrismRA arm and the external control arm, respectively.

Table 1. Study power for comparing proportion of patients with improvement in CDAI from baseline by at least MID between the two study arms

Sample size in the PrismRA arm before attrition	Sample size in the external control arm before attrition	Proportion of patients in the PrismRA arm with MID improvement in CDAI	Proportion of patients in the external control arm with MID improvement in CDAI	PrismRA arm, attrition			
				30%	35%	40%	45%
				Study power			
600	1,000	0.45	0.35	86%	84%	82%	80%
600	1,000	0.40	0.30	87%	86%	84%	82%
600	1,000	0.35	0.25	90%	89%	87%	85%
600	1,500	0.45	0.35	91%	90%	88%	86%
600	1,500	0.40	0.30	92%	91%	89%	88%
600	1,500	0.35	0.25	94%	93%	92%	90%
600	2,000	0.45	0.35	93%	92%	90%	88%
600	2,000	0.40	0.30	95%	93%	92%	90%
600	2,000	0.35	0.25	96%	95%	94%	92%

The sample size calculation was performed with SAS (version 9.4, Cary, NC).

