5.3 Data Summarization and Analysis

Summary statistics for continuous variables to be reported will include mean, median, standard deviation (SD), 25th and 75th percentile. Categorical variables will be reported using counts and proportions. Hypothesis testing will be two-sided with an alpha level of 5%. For all outcome measures, point estimates as well as two-sided 95% confidence intervals (CIs) will be provided. P-values will be reported where appropriate to four decimal points unless all p-values in a table are greater than 0.01 in which case p-values will be reported to three decimal points in that table as the fourth decimal point is not needed. Details of the specific analytic methods are described below (Section 6).

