Study endpoint	PrismRA	Control	Odds ratio (95% CI)
CDAI MID at 24 weeks	n/N (%)	n/N (%)	x.xx (x.xx-x.xx)
CDAI MID at 12 weeks	n/N (%)	n/N (%)	x.xx (x.xx-x.xx)
CDAI LDA or Remission at 24 weeks	n/N (%)	n/N (%)	x.xx (x.xx-x.xx)
CDAI LDA or Remission at 12 weeks	n/N (%)	n/N (%)	x.xx (x.xx-x.xx)
PtGA MCID at 24 weeks	n/N (%)	n/N (%)	x.xx (x.xx-x.xx)
PtGA MCID at 12 weeks	n/N (%)	n/N (%)	x.xx (x.xx-x.xx)
RAPID3 MCID at 24 weeks	n/N (%)	n/N (%)	x.xx (x.xx-x.xx)
RAPID3 MCID at 12 weeks	n/N (%)	n/N (%)	x.xx (x.xx-x.xx)
Pain VAS MCID at 24 weeks	n/N (%)	n/N (%)	x.xx (x.xx-x.xx)
Pain VAS MCID at 12 weeks	n/N (%)	n/N (%)	x.xx (x.xx-x.xx)
ACR50 at 24 weeks	n/N (%)	n/N (%)	x.xx (x.xx-x.xx)
ACR50 at 12 weeks	n/N (%)	n/N (%)	x.xx (x.xx-x.xx)

Programmer note: N= number of patients with moderate or high disease activity; n= number of patients achieving endpoint criteria

The following Tables will be created using the same layout as Table 2.1.

Table 2.1.1 Primary and secondary composite strategy study endpoints for modified ITT cohort by study arm for TNFi-naïve group

Table 2.1.2 Primary and secondary composite strategy study endpoints for modified ITT cohort by study arm for TNFi-exposed group

Table 2.2 Primary and secondary treatment policy strategy study endpoints for modified ITT cohort by study arm

Table 2.2.1 Primary and secondary treatment policy strategy study endpoints for modified ITT cohort by study arm for TNFi-naïve group

Table 2.2.2 Primary and secondary treatment policy strategy study endpoints for modified ITT cohort by study arm for TNFi-exposed group

Table 2.3 Primary and secondary composite strategy study endpoints for PrismRA-adherent cohort by study arm

Table 2.4 Primary and secondary treatment policy strategy study endpoints for PrismRA-adherent cohort by study arm

Table 3.1 CDAI change from baseline at 12 and 24 weeks for modified ITT cohort by study arm

Characteristic		PrismRA N = xxx	Control N = xxx	Average difference (95% CI)
CDAI at baseline	n	xxx	xxx	
	Mean (s.d.)	xxx (xx.x)	xxx (xx.x)	xxx (xxx-xxx)
	Median (Q1-Q3)	xxx (xxx-xxx)	xxx (xxx-xxx)	
CDAI at 12 weeks	n	xxx	xxx	
	Mean (s.d.)	xxx (xx.x)	xxx (xx.x)	xxx (xxx-xxx)
	Median (Q1-Q3)	xxx (xxx-xxx)	xxx (xxx-xxx)	
Change in CDAI at 12 weeks	n	xxx	xxx	
	Mean (s.d.)	xxx (xx.x)	xxx (xx.x)	xxx (xxx-xxx)
	Median (Q1-Q3)	xxx (xxx-xxx)	xxx (xxx-xxx)	
CDAI at 24 weeks	n	xxx	xxx	
	Mean (s.d.)	xxx (xx.x)	xxx (xx.x)	xxx (xxx-xxx)
	Median (Q1-Q3)	xxx (xxx-xxx)	xxx (xxx-xxx)	

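### Effects in TNFi-naive and TNFi-exposed patients are tabulated separately with no contrast between them, so nothing planned supports or guards against a statement that the test works in one group only

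*SAP*

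**What the plan says.** SAP 7.0 is a single sentence. For the primary outcome and secondary outcomes a to f, subgroup analyses by prior TNFi exposure "will be performed for the eligible patients who meet inclusion and exclusion criteria and initiated the study treatment". It names no interaction test and no comparison of the two subgroup effects.

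The shells in SAP 10.0 follow the same pattern. Each subgroup has its own table, for example "Table 2.1.2 Primary and secondary composite strategy study endpoints for modified ITT cohort by study arm for TNFi-exposed group", with a twin (Table 2.1.1) for TNFi-naive patients. Tables 2.2.1/2.2.2 and 3.1.1/3.1.2 are paired in the same way. The layout has the result per arm, then an odds ratio (or average difference) with its 95% CI. There is no between-subgroup column and no p-value column.

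The outcome model in SAP 6.3.1, step 5, contains arm and covariates. The only interactions mentioned in the SAP are covariate terms in the propensity score model (SAP 6.3). The Protocol has no subgroup section.

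Prior TNFi exposure is nevertheless prominent. It defines the matching strata in SAP 6.3, and Protocol 5.1 reports the test's earlier predictive performance separately: odds ratios of 3.4-8.8 in targeted-therapy-naive patients and "3.3-26.6 for TNFi-exposed patients".

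**The concern.** This is the only subgroup factor in the plan, and the Introduction already splits the test's track record along it. Those earlier odds ratios describe prediction of non-response, not the benefit of test-guided treatment, but they make the question of where the test helps a natural one.

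Two separate intervals do not answer it. Whether each effect differs from zero is a different question from whether the two effects differ from each other, and a pair with one interval clear of the null and one not is weak evidence of a difference. At stake is the description of the population in which the test is useful. The primary estimate is not affected.

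**Working it through.** **Inputs.**
- Planned size and power: "With a sample size of 600 in the PrismRA arm and 1,500 in the external control arm, the study has 88% power" (SAP 5.1).
- Response rates: "CDAI by MID are 40% and 30% in the PrismRA arm and the external control arm, respectively" (SAP 5.1).
- Week 24 attrition: "can be up to 45% in the PrismRA arm and up to 50% in the external control arm" (SAP 5.1).
- Test behind the stated power: Fisher's "exact test of independent proportions" (SAP 5.1), two-sided 5%.
- Matched controls: SAP 6.3 targets about two per PrismRA patient, so 1,200, or 600 after 50% attrition.
- Split between TNFi-naive and TNFi-exposed: not in the documents. Assumed, and varied from 50:50 to 80:20.

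**Step 1. Reproduce the plan's figure.** Evaluable patients: 600 × 0.55 = 330 and 1,500 × 0.50 = 750. SE = √(0.4×0.6/330 + 0.3×0.7/750) = 0.0317. Power = Φ(0.10/0.0317 − 1.96) = Φ(1.19) = 88.3%. Exact enumeration of Fisher's test gives 88.4%. The stated 88% reproduces.

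**Step 2. Power in each subgroup, same true 40% vs 30% in both.** With a share f of both arms, power = Φ(0.10√f/SE − 1.96). Example at 330 vs 600 and an even split (165 vs 300): SE = 0.0464, 0.10/0.0464 = 2.154, power = Φ(0.194) = 57.7%.

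**Step 3. Chance that exactly one interval excludes no effect.** With subgroup powers a and b, P = a(1−b) + b(1−a). In the example, 2 × 0.577 × 0.423 = 48.8%; both intervals exclude no effect only 0.577² = 33% of the time.

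| Patients analysed (PrismRA vs control) | 50:50 | 60:40 | 70:30 | 80:20 |
|---|---|---|---|---|
| 330 vs 600 (planned attrition, 2:1 matched) | 48.8% | 50.4% | 55.1% | 62.5% |
| 330 vs 750 (planned attrition, 1,500 controls) | 47.8% | 49.5% | 54.6% | 62.7% |
| 420 vs 750 (30% PrismRA attrition) | 43.6% | 45.8% | 52.1% | 62.1% |
| 600 vs 1,200 (no information lost) | 27.1% | 30.0% | 38.9% | 53.5% |
| 600 vs 1,500 (no information lost) | 24.0% | 27.0% | 36.1% | 51.3% |

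For 330 vs 750, Fisher's exact test gives 48, 50, 55 and 64%, and a simulation of 200,000 runs with Wald tests on the log odds ratio gives 47, 49, 54 and 62%. If neither subgroup has an effect, P = 2 × 0.05 × 0.95 = 9.5%.

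**Step 4. What the contrast would do.** In each subgroup Var(log OR) = 1/(n₁p₁) + 1/(n₁(1−p₁)) + 1/(n₂p₂) + 1/(n₂(1−p₂)), and the SE of the difference in log odds ratios is the square root of the sum of the two variances. In the same simulation, with identical effects, the contrast was significant 4.8-5.0% of the time.

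Its power is limited. Take one subgroup with OR (0.4×0.7)/(0.6×0.3) = 1.56 (log 0.442) and the other with OR 1.0, using the variances above as an approximation:
- 330 vs 750, 50:50: SE 0.276; power about 36%; ratio of odds ratios needed for 80% power, exp(2.80 × 0.276), about 2.2.
- 330 vs 600, 80:20: SE 0.358; power about 23%; ratio needed about 2.7.

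**The case against.** The strongest reply is that the harm depends on a reading the SAP never announces. Section 7.0 sets no subgroup hypothesis, no success rule and no claim that effects differ, and the shells show intervals without p-values. A reader might infer that the study plans to declare the test effective in one group and not the other, or that it will make a false subgroup claim about half the time. The documents support neither. The percentages describe how often the two tables would look discordant, not how often a claim would follow.

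Second, little information is lost. The subgroups share no patients and both odds ratios will be printed with intervals, so a reader could approximate the ratio. That largely stands, but the result would be approximate: imputation models are fitted per arm across both strata (SAP 5.4), so the two estimates are not strictly independent.

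Third, the figure near one half is conditional. It uses the ceiling attrition, whereas the primary analysis imputes missing outcomes for all eligible initiators, and the SAP's own power table runs PrismRA attrition down to 30%. This stands and is why a range is given. Imputation can move the figure towards the no-loss rows but not past them.

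Fourth, the contrast will often be inconclusive. True, but a wide interval on the ratio shows openly how little two separate tables can say about a difference.

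**Conclusion.** The gap is real and of modest importance. No contrast between TNFi-naive and TNFi-exposed effects is planned anywhere, so the study would have no prespecified basis for saying that the benefit differs, and nothing that discourages saying so.

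Its size rests on three assumptions: the planned 10-point effect is true in both groups, the amount of information lost to missing outcomes, and a split that the documents do not state. Under the first, discordant intervals arise about 48-55% of the time at planned attrition for splits of 50:50 to 70:30, about 62-63% at 80:20, and about 24-39% for 50:50 to 70:30 with no information lost. Without an effect in either group the figure is about 10%. The main analysis and its conclusion are untouched. This is a worthwhile improvement, not a defect that threatens the study.

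**What to change.** In SAP 7.0, fit the weighted outcome model of SAP 6.3.1 on the stratified matched cohort with an arm-by-prior-TNFi term in each imputed dataset, and pool it by Rubin's rule. Take both subgroup effects from that model so that they agree with the contrast. Report the ratio of odds ratios (for CDAI change, the difference between the two mean differences) with its 95% CI beside the subgroup estimates, at least for the primary endpoint.

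Add a short statement that a difference between subgroups is claimed only on this contrast; that its power is low (about 23-36% if one group has OR 1.56 and the other OR 1.0, with a ratio of about 2.2-2.7 needed for 80% power); and that a non-significant contrast does not show equal effects.

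The cost is one model term, one table column and two or three sentences. Matching is already within these strata, and imputation is run by arm with previous TNFi use among the covariates, so the imputed data can carry a difference in effect between the groups. No new cohort or data are needed.

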8.0 CONSIDERATIONS FOR FUTURE ANALYSES

MI for missing data is performed under the assumption that data are MAR. This assumption is sensitive to (1) differential rate of discontinuation between study arms that is also related to prognostic factors (e.g., informative drop-out) and (2) the possibility of unmeasured confounders. To assess the robustness of the MAR assumption sensitivity analyses may be performed. To analyze the sensitivity of treatment effect estimates to informative drop-out, missing outcomes are first imputed for completed visits and missed or out-of-window visits that occur prior to study drop-out. Any remaining missing outcomes occurring due to drop-out will

be accounted for using inverse probability of censoring weights (IPCW). [33-35] The IPCW method is a regression approach that assigns weights to each individual based on the inverse of the estimated probability of having complete follow-up data. A logistic regression model is used to predict the probability of having missing outcome data conditional on baseline and time-varying covariates at available follow-up visits. The IPCW are subsequently applied to individuals with complete (observed and imputed) data in outcome models creating a pseudo-population such that the inference is with respect to the original full cohort. [31] For outcome models using inverse probability of treatment weights (IPTW) and IPCW methods simultaneously, the individual weights are multiplied, and the resulting weighted treatment effect estimate is referred to as an inverse-probability-of-treatment-and-censoring weighted estimate (IPTCW). [25] To assess robustness of the modeling assumptions to different missing data mechanisms (e.g., not MAR), a “tipping-point” analysis [36] may be conducted that test a series of pre-determined alternative assumptions for reasons outcome data are missing during follow-up.

10.0 SHELLS FOR TABLES, FIGURES, AND LISTINGS

Figure 1 Patient flow and attrition diagram by study arm

Table 1.1 Baseline characteristics of modified ITT cohort by study arms before PSM

Characteristic		PrismRA N = xxx	Control N = xxx	SMD
Age in years	n	xxx	xxx	x.xx
	Mean (s.d.)	xxx (xx.x)	xxx (xx.x)	
	Median (Q1-Q3)	xxx (xxx-xxx)	xxx (xxx-xxx)	
Sex	Female	xxx (xx%)	xxx (xx%)	x.xx
	Male	xxx (xx%)	xxx (xx%)	
Race	Black	xxx (xx%)	xxx (xx%)	
	White	xxx (xx%)	xxx (xx%)	
	Other	xxx (xx%)	xxx (xx%)	
	Unknown	xxx	xxx	
Ethnicity	Hispanic	xxx (xx%)	xxx (xx%)	x.xx
	Non-Hispanic	xxx (xx%)	xxx (xx%)	
	Unknown	xxx	xxx	
Census region	Midwest	xxx (xx%)	xxx (xx%)	x.xx
	Northeast	xxx (xx%)	xxx (xx%)	
	South	xxx (xx%)	xxx (xx%)	
	West	xxx (xx%)	xxx (xx%)	
	Unknown	xxx	xxx	
BMI, kg/m ²	n	xxx	xxx	x.xx
	Mean (s.d.)	xxx (xx.x)	xxx (xx.x)	
	Median (Q1-Q3)	xxx (xxx-xxx)	xxx (xxx-xxx)	
Smoking status	Current	xxx (xx%)	xxx (xx%)	x.xx
	Former	xxx (xx%)	xxx (xx%)	
	Never	xxx (xx%)	xxx (xx%)	
	Unknown	xxx	xxx	
Comorbidities¹				
Lung disease	Yes	xxx (xx%)	xxx (xx%)	x.xx
	No	xxx (xx%)	xxx (xx%)	
Myocardial infarction	Yes	xxx (xx%)	xxx (xx%)	x.xx
	No	xxx (xx%)	xxx (xx%)	

Other cardiovascular	Yes	xxx (xx%)	xxx (xx%)	x.xx
	No	xxx (xx%)	xxx (xx%)	
Stroke	Yes	xxx (xx%)	xxx (xx%)	x.xx
	No	xxx (xx%)	xxx (xx%)	
Hypertension	Yes	xxx (xx%)	xxx (xx%)	x.xx
	No	xxx (xx%)	xxx (xx%)	
Fractures (spine, hip, or leg)	Yes	xxx (xx%)	xxx (xx%)	x.xx
	No	xxx (xx%)	xxx (xx%)	
Depression	Yes	xxx (xx%)	xxx (xx%)	x.xx
	No	xxx (xx%)	xxx (xx%)	
Diabetes mellitus	Yes	xxx (xx%)	xxx (xx%)	x.xx
	No	xxx (xx%)	xxx (xx%)	
Ulcer or stomach problem	Yes	xxx (xx%)	xxx (xx%)	x.xx
	No	xxx (xx%)	xxx (xx%)	
Fibromyalgia	Yes	xxx (xx%)	xxx (xx%)	x.xx
	No	xxx (xx%)	xxx (xx%)	
RDCI	n	xxx	xxx	x.xx
	Mean (s.d.)	xxx (xx.x)	xxx (xx.x)	
	Median (Q1-Q3)	xxx (xxx-xxx)	xxx (xxx-xxx)	
RA Characteristics				
Duration of RA (years)	n	xxx	xxx	x.xx
	Mean (s.d.)	xxx (xx.x)	xxx (xx.x)	
	Median (Q1-Q3)	xxx (xxx-xxx)	xxx (xxx-xxx)	
Seropositivity ²	Positive	xxx (xx%)	xxx (xx%)	x.xx
	Negative	xxx (xx%)	xxx (xx%)	
CDAI at baseline	n	xxx	xxx	x.xx
	Mean (s.d.)	xxx (xx.x)	xxx (xx.x)	
	Median (Q1-Q3)	xxx (xxx-xxx)	xxx (xxx-xxx)	
Previous use of TNFi	Yes	xxx (xx%)	xxx (xx%)	x.xx
	No	xxx (xx%)	xxx (xx%)	
Concurrent RA Medications				
Methotrexate	Yes	xxx (xx%)	xxx (xx%)	x.xx
	No	xxx (xx%)	xxx (xx%)	
Folic acid	Yes	xxx (xx%)	xxx (xx%)	x.xx
	No	xxx (xx%)	xxx (xx%)	
Non-methotrexate major csDMARDs	Yes	xxx (xx%)	xxx (xx%)	x.xx
	No	xxx (xx%)	xxx (xx%)	

Glucocorticoids	Yes	xxx (xx%)	xxx (xx%)	x.xx
	No	xxx (xx%)	xxx (xx%)	

Footnotes

¹ Using all available data before the index date comorbidities are based on the presence of at least two diagnostic codes at least 30 days apart in the external control arm; based on an additional questionnaire in the PrismRA arm.

² Rheumatoid factor or anti-citrullinated peptide antibody.

The following tables will be created using the same layout as Table 1.1.

Table 1.2 Baseline characteristics of modified ITT cohort by study arms after PSM

Table 1.1.1 Baseline characteristics of modified ITT cohort by study arms for TNFi-naïve group before PSM

Table 1.1.2 Baseline characteristics of modified ITT cohort by study arms for TNFi-exposed group before PSM

[figure not shown]
Table 1.2.1 Baseline characteristics of modified ITT cohort by study arms for TNFi-naïve group after PSM

Table 1.2.2 Baseline characteristics of modified ITT cohort by study arms for TNFi-exposed group after PSM

Table 1.3 Baseline characteristics of PrismRA-adherent cohort by study arms before PSM

Table 1.4 Baseline characteristics of PrismRA-adherent cohort by study arms after PSM

Figure 2.1 PS overlap for modified ITT cohort before and after PSM

Programmer note: The figure above is an example figure showing propensity score distributions by study arm before (left panel) and after (right panel) matching.

[figure not shown]
The following figures will be created using the same layout as Figure 2.1.

Figure 2.1.1 PS overlap for modified ITT cohort for TNFi-naïve group before and after PSM

Figure 2.1.2 PS overlap for modified ITT cohort for TNFi-exposed group before and after PSM

Figure 2.2 PS overlap for PrismRA-adherent cohort before and after PSM

Figure 3.1 Baseline covariate balance plots for modified ITT cohort before and after PSM

Programmer note: The figure above is an example figure showing absolute standardized differences before (diamond) and after (circle) matching.

The following figures will be created using the same layout as Figure 3.1.

Figure 3.1.1 Baseline covariate balance plots for modified ITT cohort for TNFi-naïve group before and after PSM

Figure 3.1.2 Baseline covariate balance plots for modified ITT cohort for TNFi-exposed group before and after PSM

Figure 3.2 Baseline covariate balance plots for PrismRA-adherent cohort before and after PSM

Table 2.1 Primary and secondary composite strategy study endpoints for modified ITT cohort by study arm

Study endpoint	PrismRA	Control	Odds ratio (95% CI)
CDAI MID at 24 weeks	n/N (%)	n/N (%)	x.xx (x.xx-x.xx)
CDAI MID at 12 weeks	n/N (%)	n/N (%)	x.xx (x.xx-x.xx)
CDAI LDA or Remission at 24 weeks	n/N (%)	n/N (%)	x.xx (x.xx-x.xx)
CDAI LDA or Remission at 12 weeks	n/N (%)	n/N (%)	x.xx (x.xx-x.xx)
PtGA MCID at 24 weeks	n/N (%)	n/N (%)	x.xx (x.xx-x.xx)
PtGA MCID at 12 weeks	n/N (%)	n/N (%)	x.xx (x.xx-x.xx)
RAPID3 MCID at 24 weeks	n/N (%)	n/N (%)	x.xx (x.xx-x.xx)
RAPID3 MCID at 12 weeks	n/N (%)	n/N (%)	x.xx (x.xx-x.xx)
Pain VAS MCID at 24 weeks	n/N (%)	n/N (%)	x.xx (x.xx-x.xx)
Pain VAS MCID at 12 weeks	n/N (%)	n/N (%)	x.xx (x.xx-x.xx)
ACR50 at 24 weeks	n/N (%)	n/N (%)	x.xx (x.xx-x.xx)
ACR50 at 12 weeks	n/N (%)	n/N (%)	x.xx (x.xx-x.xx)

Programmer note: N= number of patients with moderate or high disease activity; n= number of patients achieving endpoint criteria

The following Tables will be created using the same layout as Table 2.1.

Table 2.1.1 Primary and secondary composite strategy study endpoints for modified ITT cohort by study arm for TNFi-naïve group

Table 2.1.2 Primary and secondary composite strategy study endpoints for modified ITT cohort by study arm for TNFi-exposed group

Table 2.2 Primary and secondary treatment policy strategy study endpoints for modified ITT cohort by study arm

Table 2.2.1 Primary and secondary treatment policy strategy study endpoints for modified ITT cohort by study arm for TNFi-naïve group

Table 2.2.2 Primary and secondary treatment policy strategy study endpoints for modified ITT cohort by study arm for TNFi-exposed group

Table 2.3 Primary and secondary composite strategy study endpoints for PrismRA-adherent cohort by study arm

Table 2.4 Primary and secondary treatment policy strategy study endpoints for PrismRA-adherent cohort by study arm

Table 3.1 CDAI change from baseline at 12 and 24 weeks for modified ITT cohort by study arm

Characteristic		PrismRA N = xxx	Control N = xxx	Average difference (95% CI)
CDAI at baseline	n	xxx	xxx	
	Mean (s.d.)	xxx (xx.x)	xxx (xx.x)	xxx (xxx-xxx)
	Median (Q1-Q3)	xxx (xxx-xxx)	xxx (xxx-xxx)	
CDAI at 12 weeks	n	xxx	xxx	
	Mean (s.d.)	xxx (xx.x)	xxx (xx.x)	xxx (xxx-xxx)
	Median (Q1-Q3)	xxx (xxx-xxx)	xxx (xxx-xxx)	
Change in CDAI at 12 weeks	n	xxx	xxx	
	Mean (s.d.)	xxx (xx.x)	xxx (xx.x)	xxx (xxx-xxx)
	Median (Q1-Q3)	xxx (xxx-xxx)	xxx (xxx-xxx)	
CDAI at 24 weeks	n	xxx	xxx	
	Mean (s.d.)	xxx (xx.x)	xxx (xx.x)	xxx (xxx-xxx)
	Median (Q1-Q3)	xxx (xxx-xxx)	xxx (xxx-xxx)	
Change in CDAI at 24 weeks	n	xxx	xxx	
	Mean (s.d.)	xxx (xx.x)	xxx (xx.x)	xxx (xxx-xxx)
	Median (Q1-Q3)	xxx (xxx-xxx)	xxx (xxx-xxx)	

The following Tables will be created using the same layout as Table 3.1.

Table 3.1.1 CDAI change from baseline at 12 and 24 weeks for modified ITT cohort by study arm for TNFi-naïve group

Table 3.1.2 CDAI change from baseline at 12 and 24 weeks for modified ITT cohort by study arm for TNFi- exposed group

Table 3.2 CDAI change from baseline at 12 and 24 weeks for PrismRA-adherent cohort by study arm

The following Table will be created using the same layout as Table 2.1.

Table 4 Sensitivity analyses of primary and secondary composite strategy study endpoints for modified ITT cohort by study arm
